drainage tube) within the two weeks prior to randomisation, excluding ascites;

5) Patients with clinically symptomatic ascites requiring paracentesis or drainage, or those who have undergone ascites drainage within the past 3 months (excluding those with only imaging-detected minimal ascites that is controllable and asymptomatic);

6) Known interstitial lung disease, except for interstitial changes visible only on imaging studies;

7) Known peripheral neuropathy (CTCAE \geq Grade 3);

8) Known dihydrofolate reductase deficiency (low activity) or absence;

9) Severe infection (CTCAE > Grade 2) within 4 weeks prior to enrolment, such as severe pneumonia requiring hospitalisation, bacteraemia, or infection-related complications; symptoms or signs of infection requiring intravenous antibiotic treatment within 2 weeks prior to randomisation (excluding prophylactic antibiotic use);

10) Received any of the following treatments:

- Concomitant medications containing strong inhibitors/inducers of CYP3A4, CYP2C8, or strong inhibitors of UGT1A1 within 2 weeks prior to enrolment;

- Received radiation therapy within 2 weeks prior to enrolment;

- Undergone major surgery (e.g., thoracotomy, laparotomy, etc.) within 4 weeks prior to enrolment;

- Received treatment with any other investigational drugs within 4 weeks prior to enrolment, unless it was an observational (non-interventional) clinical study or follow-up for an interventional clinical study.

11) Abnormal coagulation function, bleeding tendency, or currently receiving thrombolytic or anticoagulant therapy. Prophylactic use of

low-dose aspirin (≤ 100 mg/day) or low-molecular-weight heparin (enoxaparin 40 mg/day or equivalent doses of other low-molecular-weight heparins) is permitted;

12) Uncontrolled cardiac symptoms or diseases, such as: (1) NYHA class 2 or higher heart failure; (2) unstable angina; (3) myocardial infarction within the past 6 months; (4) clinically significant supraventricular or ventricular arrhythmias requiring treatment or intervention;

13) History of malignant tumours other than pancreatic cancer within the past 5 years prior to enrolment, excluding adequately treated cervical carcinoma in situ, basal cell carcinoma, or squamous cell carcinoma of the skin;

14) Known allergy to irinotecan liposome, other liposome products, oxaliplatin, 5-FU, calcium folinate, adebepilumab, or any component of the aforementioned products;

Each treatment cycle lasts 14 days,with a total of 4 cycles.All medications are administered on Day 1.If the patient is known to be a homozygous carrier of the UGT1A1*28/*6 mutation,the starting dose of irinotecan liposome is reduced by one level (47 mg/m²).If no adverse reactions occur during the first cycle,the dose is increased to the starting dose level for subsequent cycles if the patient has not undergone genotyping,no initial dose adjustment is made,and haematological toxicity and diarrhoea incidence should be monitored during the study.The above chemotherapy doses are recommended doses;investigators may determine the initial dose based on the patient's tolerance.

Concurrent short-course radiotherapy:

Stereotactic body radiation therapy (SBRT)is used,targeting only the primary tumour and metastatic lymph nodes,without prophylactic irradiation of adjacent lymph nodes.The total dose is 25 Gy,administered as 5 Gy/fraction over 5 fractions.

The specific treatment process is as follows:

七、 Observation items

1. Primary efficacy endpoints

- R0 resection rate, defined as the proportion of participants assessed as having achieved R0 resection postoperatively.

2. Secondary efficacy endpoints

- OS, defined as the time from the start of treatment to death from any cause;
- EFS, defined as the time from randomisation to the first occurrence of tumour progression rendering surgery impossible, postoperative recurrence/metastasis, or death;
- Objective response rate (ORR) assessed by investigators according to RECIST v1.1 criteria, defined as the proportion of participants with the best overall response of complete response (CR) or partial response (PR). If a response of CR or PR is achieved, participants must undergo a follow-up evaluation 4 weeks after the initial assessment to confirm the response;
- PCR, defined as the absence of residual tumour cells in the resected primary tumour or sampled lymph nodes following neoadjuvant therapy;
- Safety endpoints: adverse events (AE)/serious adverse events (SAE) (assessed according to NCI-CTCAE 5.0 criteria), etc.

八、 Efficacy evaluation criteria

1. Efficacy Evaluation

Efficacy endpoints include R0 resection rate (primary endpoint), EFS, OS, ORR, and pCR rate.

2. Efficacy Evaluation Methods

This study uses RECIST 1.1 to evaluate tumour response/progression in participants; postoperative pathological specimens are used to assess R0 resection rate and pCR rate, with evaluation criteria detailed in Appendix 1.

3. Safety Evaluation

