1. Primary objective: The primary endpoint is the R0 resection rate in patients with resectable or borderline resectable pancreatic cancer with high-risk factors treated with irinotecan liposome, 5-fluorouracil/calcium folinate, oxaliplatin, and adabelimab combined with radiotherapy, defined as the proportion of participants assessed as having achieved R0 resection postoperatively.

2. Secondary objectives:

- PCR, defined as the absence of residual tumour cells in the primary tumour or sampled lymph nodes following surgery after neoadjuvant therapy.
- EFS, defined as the time from randomisation to the first occurrence of tumour progression rendering surgery impossible, postoperative recurrence/metastasis, or death, whichever occurs first;
- OS, defined as the time from the start of treatment to death from any cause;
- ORR, as assessed by the investigator according to RECIST v1.1 criteria, defined as the proportion of participants with the best overall response of CR or PR. If the response is CR or PR, participants must undergo a follow-up evaluation 4 weeks after the initial assessment;
- Safety endpoints: adverse events (AE)/serious adverse events (SAE) (assessed according to NCI-CTCAE 5.0 criteria), etc.

四 、 Study design type, principles, and trial procedures

1. Study Design

This study is a prospective, single-arm, exploratory study aimed at evaluating the efficacy and safety of irinotecan liposome, 5-fluorouracil/calcium folinate, oxaliplatin, and adabelimab in combination with radiotherapy for resectable or borderline resectable pancreatic cancer with high-risk factors, with a planned enrolment of 37 patients.

After screening and meeting the inclusion and exclusion criteria, patients who signed informed consent will receive neoadjuvant therapy with irinotecan liposome, 5-fluorouracil/calcium folinate, oxaliplatin, and adabelimab (every 2 weeks, with 2 weeks as one cycle) for a total of 4 cycles of preoperative chemotherapy combined with immunotherapy, concurrently with 5 sessions of short-course radiotherapy:

- Patients assessed as eligible for curative surgery via abdominal contrast-enhanced CT/MRI undergo surgery within 10 – 20 days after completion of neoadjuvant therapy. An abdominal contrast-enhanced CT/MRI is performed 4 – 6 weeks post-surgery, and the adjuvant therapy regimen is determined by the investigator;

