- For patients assessed by abdominal contrast-enhanced CT/MRI as ineligible for curative surgical resection, the investigator may select a subsequent treatment regimen based on their judgment, and patients will continue to be followed up until disease progression, inability to tolerate toxic side effects, or withdrawal of informed consent.

Safety visits: After enrolment, safety visits will be conducted on Day 1 of each treatment cycle prior to surgery, on Day 1 of each treatment cycle post-surgery, and at the end of treatment. Safety visits will be conducted every 12 weeks post-treatment (including blood counts and

liver/kidney function tests). Survival follow-up will be conducted every 3 months.

Imaging assessment: All lesions will be recorded and assessed according to RECIST v1.1. Unless otherwise specified, the permissible window period for imaging examinations is ± 7 days. During the study period, unscheduled imaging examinations may be conducted when tumour recurrence or metastasis is suspected.

Screening period: Imaging studies of the chest, abdomen, and pelvis are required. The abdomen and pelvis must undergo contrast-enhanced MRI/CT scans (slice thickness ≤ 5 mm), and the chest must undergo CT scans (slice thickness ≤ 5 mm). Patients suspected of having brain metastases must also undergo contrast-enhanced MRI/CT of the head to rule out brain metastases. When bone metastasis is confirmed or clinically suspected, bone scan examinations are required to rule out bone metastasis. Assessment of tumour baseline must be conducted within 2 weeks prior to randomisation. If the investigator determines that imaging examinations can represent the subject's baseline status, the baseline imaging examinations may be extended to within 4 weeks prior to enrolment;

Neoadjuvant therapy: After completing 4 cycles of preoperative neoadjuvant chemotherapy + short-course radiotherapy, an abdominal (enhanced MRI/enhanced CT) examination is performed. If metastasis to other sites is suspected, additional imaging examinations of those sites are required, preferably under the same conditions as the screening period, including scanning method, slice thickness, and contrast agent use;

Postoperative: Within 4 – 6 weeks post-surgery, perform abdominal imaging (enhanced MRI/enhanced CT). If metastasis to other sites is suspected, additional imaging studies of those sites should be conducted;

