2.7. Abnormal liver function tests

If abnormal AST and/or ALT levels are accompanied by an abnormal increase in total bilirubin levels, and the following conditions (1), (2), and (3) are met without any other identifiable cause, such cases should be reported as important medical events and reported according to the SAE procedure.

- Abnormal ALT or AST

Baseline normal: ALT or AST $> 3 \times$ ULN during treatment;

Baseline abnormal: During treatment, ALT or AST $> 2 \times$ s of baseline levels, and values $> 3 \times$ s of ULN; or values $> 8 \times$ s of ULN.

- TBIL abnormalities

Baseline normal: Treatment-period TBIL $> 2 \times$ ULN;

Baseline abnormal: Treatment-period TBIL increase $> 1 \times$ ULN or value $> 3 \times$ ULN.

- No haemolysis, and alkaline phosphatase $< 2 \times$ ULN (or information not available)

If a patient experiences abnormal AST and/or ALT levels concurrent with an abnormal increase in total bilirubin levels during the safety follow-up period, it is recommended that the patient return to the research centre for evaluation and confirmation as soon as possible (preferably within 48 hours) after the abnormal results are known.

十、 Quality control and quality assurance of the study

Statistical Analysis Study Flowchart

Project/Assessment Time (Window Period)	Screening period		Preoperative neoadjuvant therapy period	Surgical Treatment Period		Postoperative adjuvant therapy period	Post-treatment follow-up visit ^[33]	Follow-up period	
	Within 4 weeks prior to randomisation	Within 10 days prior to randomisation	Cycles 1–4 ^[32]	Within 1–2 weeks after the last dose of neoadjuvant therapy		Cycles 1–n (Cycle 1 begins 4–6 weeks post-surgery)		Safety follow-up period ^[34]	Tumour progression/recurrence and survival follow-up ^[35]
			CnD1 (± 3d)	Preoperative	Surgery (±3 days)	CnD1 (± 3d)	(±7 days)		
Baseline data									
Sign informed consent ^[1]	√								
Inclusion and exclusion criteria	√	√							
Demographic characteristics	√								
Tumour history ^[2]	√								
Other medical history ^[3]	√								
Laboratory Tests, Clinical Examinations/Assessments									

Project/Assessment Time (Window Period)	Screening period		Preoperative neoadjuvant therapy period	Surgical Treatment Period		Postoperative adjuvant therapy period	Post-treat ment follow-up visit ^[33]	Follow-up period	

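### The 4-week re-evaluation required for every CR or PR does not fit before surgery on the nominal schedule, and the protocol does not say how operated responders then count in ORR

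*Protocol*

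**What the plan says.** ORR is a secondary endpoint: best overall response of CR or PR by RECIST v1.1, assessed by the investigator. Two sections add a repeat assessment. Protocol section 三, Secondary objectives, has "If the response is CR or PR, participants must undergo a follow-up evaluation 4 weeks after the initial assessment". Section 七, Secondary efficacy endpoints, has the same rule and gives its purpose: "participants must undergo a follow-up evaluation 4 weeks after the initial assessment to confirm the response".

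The schedule comes from section 四 (Study Design, repeated in Study procedures) and the study flowchart:

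- Response scan: "After completing 4 cycles of preoperative neoadjuvant chemotherapy + short-course radiotherapy, an abdominal (enhanced MRI/enhanced CT) examination is performed". The flowchart's imaging row is marked at screening and preoperatively, with nothing during cycles 1–4.
- Surgery, section 四: eligible patients "undergo surgery within 10 – 20 days after completion of neoadjuvant therapy".
- Surgery, flowchart: "Within 1–2 weeks after the last dose of neoadjuvant therapy", with a tolerance of 3 days either way.
- Imaging tolerance: unless otherwise specified, "the permissible window period for imaging examinations is ± 7 days".
- Unscheduled scans are provided for suspected recurrence or metastasis. Confirming a response is not named as a reason.
- The next scheduled scan in operated patients is 4–6 weeks after surgery.

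The analysis text (section 十一, 2.2) counts patients whose best response is CR or PR and gives a Clopper-Pearson 95% interval. It does not mention confirmation. Efficacy is analysed in the ITT set.

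**The concern.** The protocol orders a site procedure that its own visit schedule leaves no room for in patients who respond and go to surgery. For such a patient a site must miss either the 4-week evaluation or the surgery window. By the next scheduled scan the primary target lesion is gone, so response can no longer be confirmed on it.

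The counting rule is then open. If sections 三 and 七 are read as requiring confirmation, operated responders drop out of the numerator. If section 十一 is followed, they stay in. Two analysts could report quite different ORRs from the same data. Under the first reading the patients who still count are mainly those not resected, who cannot be successes on the R0 primary endpoint.

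**Working it through.** The protocol states no figure for this point, so there is none to reproduce. The check compares the longest interval from first response scan to surgery with the interval that the re-evaluation needs.

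**Step 1: nominal schedule.** Because the scan follows completion of the four cycles, the most favourable case puts it on the very day from which the surgery window is counted. The longest gap is then the upper end of that window. The need is 4 × 7 = 28 days.

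| Surgery timing | Longest gap | Shortfall against 28 | Gap with +3 days for surgery | Shortfall against 28 |
|---|---|---|---|---|
| Section 四 (10–20 days after completion) | 20 | 8 | 23 | 5 |
| Flowchart (1–2 weeks after last dose) | 14 | 14 | 17 | 11 |

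The 14 days are an upper bound. With cycle 1 day 1 as day 1, the last dose is on day 1 + 3 × 14 = 43, and cycle 4 ends on day 56. Flowchart surgery falls on days 50–57. A scan at the end of cycle 4 would leave 57 − 56 = 1 day.

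**Step 2: with the imaging tolerance.** A confirmatory scan taken 7 days early needs 28 − 7 = 21 days.

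- Section 四: 20 < 21 fails; 23 ≥ 21 fits. This requires the first scan on days 0–2 after completion and surgery on days 21–23.
- Flowchart: 14 < 21 and 17 < 21; both fail.

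Moving the first scan 7 days before the anchor lengthens the gap to 27 (30 with +3) under section 四 and to 21 (24 with +3) under the flowchart. Of these only 30 reaches 28, though all four reach 21. This reading conflicts with the imaging text, which places the scan after the four cycles are complete, so it is not relied on.

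**Step 3: effect on ORR if confirmation were enforced.** The response rates and operated shares are assumptions; the protocol gives neither. N = 37 is the planned enrolment. Responders = 37 × rate, rounded (18.5 taken as 18). Confirmable = responders × (1 − operated share), rounded, treating every operated responder as unconfirmable and every other as confirmed. Confirmed ORR = confirmable / 37.

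| Assumed rate | Unconfirmed ORR (95% CI) | 60% operated | 80% operated | 100% operated |
|---|---|---|---|---|
| 20% | 7/37 = 18.9% (8.0–35.2) | 3/37 = 8.1% | 1/37 = 2.7% | 0% |
| 30% | 11/37 = 29.7% (15.9–47.0) | 4/37 = 10.8% | 2/37 = 5.4% | 0% |
| 40% | 15/37 = 40.5% (24.8–57.9) | 6/37 = 16.2% | 3/37 = 8.1% | 0% |
| 50% | 18/37 = 48.6% (31.9–65.6) | 7/37 = 18.9% | 4/37 = 10.8% | 0% |

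Intervals are Clopper-Pearson. For 0/37 the interval is 0–9.5%.

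**The case against.** The strongest reply is that the protocol never says an unconfirmed CR or PR becomes a non-response. ORR is defined by best overall response, and the 4-week sentence can be read as a separate procedural instruction; the version in section 三 does not even state that its purpose is confirmation. The analysis section counts best response without any such condition. The SAP is not shown, and the evaluation criteria are referred to an Appendix 1 that is not in the text at hand; either could settle the counting.

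This stands as far as it goes. A reader might infer that ORR as written counts only unresected responders and so runs against its own purpose. The documents do not support that as the plan's stated rule. It is one of two readings, and the table in step 3 shows its effect only if it is adopted. The reply does not remove the scheduling conflict: an SAP can decide how to count, but it cannot create a scan that the visit schedule leaves no room for.

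A reader might also infer that no operated responder can ever be confirmed. That is true on the nominal schedule, but the stacked tolerances in step 2 leave a narrow exception under the section 四 timing. That sites would delay surgery to obtain the scan is conjecture; nothing in the protocol says so.

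Finally, ORR is one of several secondary endpoints in a single-arm exploratory study with mainly descriptive analysis and no pre-specified hypotheses. This limits the weight of the point.

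**Conclusion.** The conflict is real under both stated surgery timings. With the scan after completion of the four cycles, the gap to surgery falls 8 or 14 days short of the 28 required, and 5 or 11 days short with the surgery tolerance. The only fit is a confirmatory scan a full 7 days early with surgery on days 21–23, and only under section 四. A responder who is operated on therefore essentially cannot be confirmed, and sections 三, 七 and 十一 leave open whether that patient counts.

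The size of the effect depends on which reading is used and on assumed rates. If confirmation is enforced and 20–50% respond, confirmed ORR is about 8–19% with 60% of responders operated on, 3–11% with 80% and 0% with all. If section 十一 is followed, there is no loss. The downward direction under enforcement does not depend on the assumed rates, provided some responders are operated on.

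This is a correction to a secondary endpoint. It does not touch the R0 primary endpoint or the 37 patients, and it is not a fault on which the trial's main result depends.

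**What to change.** - In sections 三 (Secondary objectives) and 七 (Secondary efficacy endpoints), define ORR as unconfirmed best overall response of CR or PR by RECIST v1.1. Use scans up to surgery for operated patients and keep later scans for unresected patients.
- Remove the 4-week confirmation requirement for patients who proceed to surgery.
- Align section 十一, 2.2 with this definition. Keep the ITT denominator and the Clopper-Pearson interval, and label the result *unconfirmed ORR*.
- If wanted, report confirmed response in unresected patients separately.
- The sponsor must reconcile the surgery timing in section 四 with that in the flowchart. This review does not say which is right.

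The cost is a short wording amendment in three places plus the timing reconciliation. The ORR change needs no extra scans and alters no treatment. The downside is that an unconfirmed ORR is somewhat more optimistic than a confirmed one, which is why the label matters.

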3.1. Surgical Safety

This includes assessing the incidence and severity of postoperative complications based on the Clavien-Dindo grading system, as well as summarising and analysing the surgical duration and hospitalisation duration of participants in the experimental and control groups.

3.2. Adverse Events

The severity of adverse events was assessed according to the CTCAE v5.0 criteria. During the trial, adverse event reports should be completed truthfully, including the type of adverse event, incidence rate, onset and resolution times, severity, relationship to the study drug, duration, measures taken, and outcome.

3.3. Other Safety Indicators

Blood, urine, and stool samples will be collected according to the trial flowchart and analysed in local laboratories. Physical examinations include height (only at baseline), head and face, skin system, lymph nodes, eyes, ears, nose, and throat, mouth, respiratory system, cardiovascular system, abdomen, genitourinary system, musculoskeletal system, nervous system, and mental status. Vital signs include temperature, blood pressure, pulse, and respiratory rate (all measured after 5 minutes of rest).

ECOG performance status.

九、 Observation of adverse events.

1. Adverse events (AE)

Adverse events (AEs) refer to adverse medical events that occur in patients after receiving a medication, but they are not necessarily causally related to the treatment. AEs can include any unfavourable, unexpected symptoms, signs, laboratory test abnormalities, or diseases, and at least include the following situations:

- Pre-existing medical conditions/diseases that worsened after the start of the study drug (including worsening of symptoms, signs, or laboratory test abnormalities) are recorded as AEs;
- Any new adverse event: any new adverse medical condition (including symptoms, signs, or newly diagnosed diseases);
- Abnormal laboratory test results with clinical significance.

Diagnostic or therapeutic invasive procedures (e.g., surgery) or non-invasive procedures should not be reported as AEs; however, if the underlying disease condition leading to such procedures meets the definition of an AE, it should be reported. For example, acute appendicitis occurring during the AE reporting period should be reported as an AE, while the appendectomy performed as a result should be recorded as the treatment method for that AE.

Researchers should document any AEs experienced by patients in detail, including: AE name, onset and resolution times, severity (grading according to the 5.0 version of the NCI CTCAE), AE-drug relationship, duration, measures taken regarding the study drug due to the AE, outcome, and whether it was a serious adverse event. All AEs occurring from the start of study drug administration until the end of the safety follow-up period should be recorded.

1.1. Criteria for assessing the severity of adverse events ()

Refer to the NCI-CTCAE Version 5.0 grading criteria for drug-related adverse events. If an AE not listed in the NCI-CTCAE Version 5.0 table occurs, the following criteria may be used:

Grade	Clinical Description of Severity
1	Mild; no clinical symptoms or only mild clinical symptoms; only clinical or laboratory abnormalities; no treatment required;
2	Moderate; requires minor, local, or non-invasive treatment; age-appropriate activities of daily living (ADL) with the use of assistive devices are limited; ADL refers to activities such as cooking, shopping, making phone calls, and counting money;
3	Severe condition or medically significant symptoms but not currently life-threatening; leading to hospitalisation or prolonged hospital stay; resulting in disability; limitations in self-care ADL. Self-care ADL includes bathing, dressing, undressing, eating, using the toilet, taking medication, etc., but not bedridden;
4	Life-threatening; Requiring emergency treatment;
5	Death related to the adverse event (AE);

Note the distinction between the severity and seriousness of adverse events. For example, "severe headache" may be classified as severe in terms of severity, but it cannot be listed as a serious adverse event (SAE) unless it meets the criteria for an SAE.

